## **STATEMENT OF COMPLIANCE**

This trial is being conducted under a Clinical Trial Application (CTA) which is ongoing with Health Canada. The trial will be conducted in accordance with Good Clinical Practice (GCP) as described in Health Canada's section C.05.010/Division 5 of the Food and Drugs Regulations, International Conference on Harmonization-Good Clinical Practice (ICH-GCP E6 R2), and Tri-Council Policy Statement (TCPS2, 2014), applicable federal, provincial and local regulatory and legislative requirements.

The Sponsor-Investigator, [name], will assure that no deviation from, or changes to the protocol will take place without prior documented authorization (i.e., a no objection letter - NOL) from Biomedical Canada (Therapeutic Products Directorate) and documented approval from the University of Manitoba (UoM) Health Research Ethics Board (BREB), except where necessary to eliminate an immediate hazard(s) to the trial participants. All personnel involved in the conduct of this study have completed the required mandatory compliance training.

The protocol, informed consent form, recruitment materials, and all participant materials will be submitted to UoM BREB for review and approval. Approval of both the protocol and the consent form will be obtained before any participant is enrolled. Any amendment to the protocol will require review and approval by the UoM BREB before the changes are implemented to the study as well as authorization from Health Canada. All changes to the consent form will be BREB approved.

## PROTOCOL SUMMARY

Title:	Using a single dose of dexamethasone at 0.6mg/kg of body weight versus 0.15 mg/kg of body weight for the treatment of croup: an internal vanguard randomized controlled non-inferiority trial.
Sponsor	The University of Manitoba
Sponsor- Investigator	[name]
Study Description:	We will conduct an internal vanguard, randomized, double-blind trial comparing treatment with dexamethasone at 0.15mg/kg to 0.6mg/kg for children with croup.
Objectives:	
-To determine a feasible sample size estimation, eligibility criteria, recruitment and retention rates and the noninferiority margin for the definitive RCT.
 
-Engage patients and families with lived experience to improve the vanguard RCT and to support designing and implementing the definitive RCT.

Outcomes:	
Primary outcome:
 
-Return visits or readmissions to the hospital within 7 days following initial presentation to the ED with croup.
 
Secondary Endpoints:
 
-Adverse events (AEs) following treatment with either of the 2 doses of dexamethasone within 7 and 30 days of treatment.
 
AEs: Disseminated varicella, gastrointestinal bleeding, unspecified bleeding, pneumonia, sepsis, febrile convulsion, bacteria tracheitis, tachycardia/fast heartbeat, and restlessness.

Study Population:	We will enroll 50 children at the Winnipeg Children's Hospital ED. We will enroll children aged 6 months – 5 years with clinical diagnosis of croup within the next 1 year. We will exclude children who are unable to tolerate or ingest oral dexamethasone, other causes of stridor, other underlying systemic diseases defined as chronic lung disease, chronic heart disease, chronic kidney disease, and immunodeficiency), recent exposure to varicella, treatment with oral or intravenous corticosteroids within the preceding 72 hours.
Phase:	Vanguard
Description of Sites/Facilities Enrolling Participants:	Health Sciences Centre Winnipeg Children's Hospital (Winnipeg),
Description of Study Intervention:	
Active Intervention: Treatment with one dose of oral dexamethasone (0.15 mg/kg per dose; maximum single dose 3 mg)
 
Active control: Treatment with one dose of oral dexamethasone (0.6 mg/kg per dose; maximum single dose 12 mg)

Study Duration:	Estimated time 12 months from when the study opens to enrolment until completion of data analyses.
Participant Duration:	Participants will be followed up when presenting to the ED within 7 and 30 days after their enrolment visit.

## SCHEDULE OF ACTIVITIES

Procedures	Enrollment Visit (Day 0)	4 hours post oral intervention or at discharge (if sooner than 4 hours)	Day 1 - 7	Day 8 - 30	Day > 30
Screening	X				
Inclusion/exclusion criteria	X				
Informed consent	X				
Demographics	X				
Medical history	X				
Vital signs	X	X			
Weight	X				
Allocation	X				
Adverse event monitoring and determination	X	X	X	X	
Chart review/electronic data base review					X
Complete Baseline Case Report Forms (CRFs)	X	X	X		
Complete follow up CRFs			X	X	
Oral dexamethasone 0.15mg/kg vs 0.6mg/kg	X				

## **INTRODUCTION**

Croup is a common childhood respiratory disease that leads to frequent emergency department (ED) visits (1). **It accounts for 7% and 3% of hospitalization in under 5 and children between 6 months-3 years in North America, respectively (2, 3).** The diagnosis of croup is clinical including sudden onset of a seal-like barking cough, often accompanied by stridor, voice hoarseness, and respiratory distress (1). While croup is a self-limiting viral infection, the burden of frequent hospitalization contributes significantly to health care utilization (4, 5). Studies have reported on the effectiveness of glucocorticoids at reducing the severity of croup, the rate and length of hospitalization, return visits, and admission to the intensive care unit for croup (6-8). However, they are associated with adverse events (AEs) (9-12).

## **RATIONALE**

**Adverse events:** A recent self-controlled case series study with over **4 million children** examined the potential harms of corticosteroid bursts (defined as courses of oral corticosteroids for 14 or fewer days) (9) and found that the most common indications for prescription of corticosteroid bursts were acute respiratory tract infections (including croup syndrome) and allergies (9). Of the AEs investigated, **GI bleeding, pneumonia, and sepsis (including bacteria tracheitis)** were directly associated with glucocorticoid bursts. The incidence rate differences per 1000 person-years between children administered a single corticosteroid burst and those not prescribed corticosteroids were 0.60 (95%CI, 0.55-0.64) for **GI bleeding**, 9.35 (95%CI, 9.19-9.51) for **pneumonia**, and 0.03 (95%CI, 0.02-0.05) for **sepsis**. Likewise, another case-control study (10) that was not statistically significant but clinically relevant sounded a note of caution on a possible increase in cases of **disseminated/complicated varicella zoster infection** with recent corticosteroid use.

**Bronchopneumonia and bacteria tracheitis** have been reported in patients treated with dexamethasone at 0.6mg/kg versus 0.15mg/kg in a randomized controlled trial (RCT) (11). Parker et al. (12) reported increased vomiting and febrile convulsion with dexamethasone at 0.6mg/kg. To date, the trials that reported on the AEs associated with using dexamethasone at 0.6mg/kg are limited, inconclusive, **but suggest that a low dose may be associated with fewer AEs (11-15).** All the RCTs were based on the frequentist approach (11-15), **which is prone to error of misinterpretation.** Bayesian methods are an alternative to the frequentist, i.e., the standard null hypothesis significance testing (NHST) framework, and they have advantages.

**Glucocorticoids:** Glucocorticoids are a class of corticosteroids with anti-inflammatory properties through which they reduce the mucosal edema and inflammation that characterize croup and, as such, reduce the associated difficulty in breathing (7). Dexamethasone is one of the long-acting systemic corticosteroids with a high glucocorticoid potency (15). A few systematic reviews have been conducted on the effectiveness of treating croup with glucocorticoids (16-19). **We just published a Cochrane systematic review (20) to address the growing debate about the effectiveness of low dose glucocorticoids to treat croup (9, 11-14).** We found that a smaller dose of dexamethasone at 0.15 mg/kg is as effective as the standard dose of dexamethasone at 0.60 mg/kg. **We also found no significant difference in return visits or readmissions** of croup patients treated with either of the doses (**relative risk [RR]=0.91, 95% CI**

**0.71 to 1.17).** Likewise, there **was no significant difference in length of stay in the hospital or ED (mean difference [MD]=0.12, 95% CI –0.32-0.56)** (20). While a few studies have compared dexamethasone at 0.6 mg/kg to 0.3mg/kg, the call to investigate dexamethasone at 0.15mg/kg of body weight is more common (14, 20). **It is clinically relevant to know the lowest dose of dexamethasone that treats croup effectively.**

**Bayesian methods:** Bayesian methods are increasing in clinical research and are particularly useful in conducting and analyzing RCTs (21, 22). This is partly due to concerns about the interpretation of results based on the NHST framework, which is prone to error (21) and susceptible to misinterpretation (23). A body of evidence have relentlessly highlighted the limitations and misconceptions of the NHST framework and *P*-values (24, 25), including interpreting a non-statistically significant difference (*P*-value >5%) between two groups to mean that the null effect is most likely. **Bayesian methods also allow the incorporation of external information into the design and analysis of the trial, this is especially important during the design phase where sample size calculations require information on effect sizes and variability** (26). Expert elicitation is one method to extract this prior knowledge and is becoming more frequent in trials. A review of 460 studies that discussed Bayesian prior elicitation found 42 studies related to clinical trial design and analysis (27). ***Expert elicitation aims to come to a clinical consensus about the current information available about the outcome of interest, encoded in a “prior distribution”. Prior distribution can be used in Bayesian sample size estimation while accounting for statistical uncertainty.***

**Patient engagement:** Engaging patients with lived experience in designing and implementing RCTs is of immense benefits. There is an increase in recognition of patient experience as one of the indicators of quality healthcare (28, 29). Evidence suggests a direct association between a good patient experience and optimal care and patient safety (30). In pediatric EDs where the diversity of patients is increasing, a shared model is especially important. None of the previous RCTs that compared the two doses considered patient voice or reported on patient engagement in designing or implementing the trial.

## HYPOTHESIS

1. Implementing a Bayesian elicitation process alongside a vanguard RCT will provide a strong basis to design a definitive noninferiority RCT of dexamethasone at 0.15mg/kg. 2. Engaging patients/parents with lived experience will help to (ensure the vanguard RCT is as best as possible for participants and) identify priority areas for families in implementing the definitive RCT.

## RESEARCH QUESTION

1. Is the definitive RCT feasible based on eligibility criteria and the recruitment process in the vanguard RCT? 2. Based on a Bayesian elicitation process, what sample size is needed for the definitive RCT to assess noninferiority of dexamethasone at 0.15mg/kg versus 0.6mg/kg using a Bayesian framework? 3. What is the noninferiority margin of treating croup with 0.15mg/kg that can be tolerated by clinicians? 4. What are the priorities of families in assessing noninferiority of dexamethasone at 0.15mg/kg versus 0.6mg/kg to treat croup?

## OVERALL GOAL

The overall goal is to reduce the AEs associated with the treatment of croup by using a low dose of dexamethasone at 0.15mg/kg. The specific objectives below will help in achieving this goal.

### SPECIFIC OBJECTIVES

The specific objectives of the studies described in this application are:

1. Implement a vanguard RCT to determine a feasible sample size estimation, eligibility criteria, recruitment and retention rates and the noninferiority margin for the definitive RCT.
2. Engage patients and families with lived experience to improve the vanguard RCT and to support designing and implementing the definitive RCT.

## METHODS AND EXPERIMENTAL APPROACHES

### Design and study site:

**This is an internal double-blinded vanguard RCT, which will be conducted at the Winnipeg Children's Hospital (WCH). The entire project is designed to plan and implement a large multicenter definitive RCT (31).** The timeline and research activities of the entire study are presented in **Table 1 and Figure 1**.

### Phase 1: Obtaining ethics approval.

We will obtain ethics approval from all relevant regulatory bodies. **Table 1** shows the list of the bodies.

### Phase 2a: Implementing an internal vanguard RCT at WCH to plan and design a multicenter definitive RCT.

The vanguard RCT aims to assess **a feasible sample size, eligibility criteria, recruitments rates, and noninferiority margin for a definitive RCT.**

### Inclusion criteria:

These are:

- Children aged **(6 months-5 years)** with clinical diagnosis of croup (1, 32).
- Presenting to the Winnipeg Children's Hospital ED

### Exclusion criteria:

These are:

- Children with body weight more than 20kg

- Children who are unable to tolerate or ingest oral dexamethasone,
- Known hypersensitivity/allergy to dexamethasone,
- Other causes of stridor (such as acute epiglottitis, bacterial tracheitis, anaphylaxis, foreign body aspiration),
- Other underlying systemic diseases defined as chronic lung disease, chronic heart disease, chronic kidney disease, and immunodeficiency),
- Recent exposure to varicella,
- Treatment with oral or intravenous corticosteroids within the preceding 72 hours.

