### **Description of Study Intervention and Outcome**

The intervention is dexamethasone at 0.15mg/kg while the active control is dexamethasone at 0.6mg/kg. The primary outcome is return visits or readmissions to the hospital within 7 days following initial presentation to the ED with croup. The secondary outcome is AEs following treatment with either of the 2 doses of dexamethasone within 7 and 30 days of treatment (Appendix A).

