### Vanguard RCT recruitment process and sample size estimation:

Based on the budget allocated for patient recruitment (**see attached budget**), sampling of children with clinical diagnosis of croup who presented to the WCH ED between January 2021 and January 2022 (**n=710**), and our experience from a similar trial that used 720 children (34), we plan to recruit 50 children within a year for this vanguard trial (Figure 1). **We will enrol 50% (25 children, in ratio 60:40% male to female) per treatment arm and assess for missing data and protocol adherence.** We will leverage a Bayesian elicitation process used by our team for an ongoing trial on bronchiolitis (35). We will elicit the probability of return visits or readmissions to ED within 7 days for each dose of dexamethasone at 0.15mg/kg versus 0.6mg/kg. The probabilities of revisits or readmissions to the ED closely reflect clinical decision making. We will then use bivariate elicitation to understand the relationship between the two probabilities (36, 37).

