## MEASURES TO MINIMIZE BIAS: RANDOMIZATION AND BLINDING

### Randomization

Computerized randomization will be performed by a statistician at the George and Fay Yee Centre for HealthCare Innovation to generate the randomization list. We will perform a computerized randomization in REDCap stratified by age (Figure 1). We will do a block randomization with random

blocks of undisclosed block sizes over the seasons to ensure that we get temporal distribution of croup cases. We will randomly assign patients into either the intervention or control in ratio 1:1. This process will help to reduce bias due to selection and residual confounding that may bias our results. Because croup season peaks over the fall and winter months in Canada, our randomization will consider this factor such that each arm will have an almost similar number per the peak season. While croup is common between 6 months and 5 years, a typical croup affects children between 6 months and 3 years. Based on this, we will randomize such that this age category (6 months-3years and >3 years – 5 years) has almost similar distribution in each arm.

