### Follow-up measurement in the ED:

The participants' parents/caregivers will not be followed up by either email or telephone following enrolment. However, the outcome assessors will collect data from patient's electronic medical records (EMR) per the follow-up CRF. The follow-up data will include date of initial presentation to ED, date of discharge at initial presentation to ED, number of return visits to the ED with 7 and 30 days, croup severity, symptoms at ED presentation, onset of symptoms, length of ED stay, discharge date, hospitalization due to croup, length of hospitalization, dose of dexamethasone, other medications (such as epinephrine, antibiotics) and the doses administered, AEs associated with the medications, will be collected at follow visits and recorded in the Follow-up CRF. We will also estimate the retention rate.

**Chart Review:** A research team member will review each participant's hospital chart once the 30-day follow-up period has elapsed to examine return ED visits, admission to hospital, diagnosis for any hospital visit, any corticosteroid treatment in hospital. All children with an admission diagnosis of croup will be considered to have been admitted for croup. All charts where an admission diagnosis is other than croup will be reviewed by the site coordinator in conjunction with qualified site investigator to determine reason for admission. We will define admission to hospital as per ICD-10 (Appendix A).

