## **Phase 2b: Determining the noninferiority margin.**

The noninferiority margin is the number of revisits/readmission for croup that clinicians can tolerate when children are treated with 0.15mg/kg versus 0.60mg/kg. To determine the noninferiority margin for dexamethasone at 0.15mg/kg, we will conduct two surveys containing case scenarios to sample ED physicians (41) (**Appendix B for details**). Implied consent will also be used for the noninferiority exercise, meaning that by agreeing to participate in the noninferiority survey, the emergency physicians agree that their data can be used for research. This will run concurrently with the vanguard RCT.

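### The 72-hour prior-steroid exclusion names only oral and intravenous routes, so a child just given an intramuscular or nebulised corticosteroid is eligible as written: a small, cheap gap to close, mainly for the definitive trial

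*Combined protocol and SAP*

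**What the plan says.** In the combined protocol and SAP, the Exclusion criteria list "Treatment with oral or intravenous corticosteroids within the preceding 72 hours". The Study Population row of the Protocol Summary repeats the rule: "treatment with oral or intravenous corticosteroids within the preceding 72 hours". The two agree, so this is the intended wording and not a slip in one place.

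The comparison is between two doses: "The intervention is dexamethasone at 0.15mg/kg while the active control is dexamethasone at 0.6mg/kg". The endpoint is clinical: "The primary outcome is return visits or readmissions to the hospital within 7 days following initial presentation to the ED with croup".

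The Screen failure section allows a child to be screened again at a later ED visit in the same croup episode. At baseline, the Efficacy Assessments section collects other medications, with epinephrine and antibiotics as examples. Corticosteroid given before enrolment, and its route, are not named. The Definitive RCT section says that the design will draw on the elicitation exercise and on patient recommendations, but also that the PICO is expected to match the vanguard's.

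**The concern.** A 72-hour look-back for corticosteroids has one evident purpose: to keep out children who are already under steroid effect when they receive the study dose. Limiting it by route leaves a hole. A site applying the text literally would enrol a child who had received an intramuscular corticosteroid elsewhere shortly before arrival, or a nebulised one. The repeat eligibility check in the Screen failure section would not stop this, because the child meets the criteria.

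What is at stake is the contrast between arms. If some children in both arms carry steroid effect from an earlier dose, any real difference in return visits is likely to be smaller among them, and the overall difference is diluted. In a superiority trial that costs power. In a noninferiority trial it makes a false claim easier.

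**Working it through.** **Is the gap closed elsewhere?** The other exclusions are weight above 20 kg, inability to take oral dexamethasone, hypersensitivity to it, other causes of stridor, chronic systemic disease and recent varicella exposure. The chronic lung disease item may remove some regular users of inhaled steroid. It does not touch a child given one intramuscular or nebulised dose for this episode. A child who returns within 72 hours of an oral study dose is excluded by the existing wording, so only the unlisted routes remain open.

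**The plan's own figure.** The sample size section says "we plan to recruit 50 children within a year for this vanguard trial", and the Randomization section says "We will randomly assign patients into either the intervention or control in ratio 1:1". So 50 × 50% = 25 per arm, as stated. The 50 rests on budget, caseload and experience. There is no power formula to reproduce, and the gap does not change the number.

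**Dose contrast (illustration).** Let d be prior steroid in dexamethasone-equivalent mg/kg, counted as still fully active. The ratio between arms is (0.6 + d)/(0.15 + d).

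| d (assumed) | Ratio |
|---|---|
| 0 | 0.60/0.15 = 4.0 |
| 0.15 | 0.75/0.30 = 2.5 |
| 0.3 | 0.90/0.45 = 2.0 |
| 0.6 | 1.20/0.75 = 1.6 |

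The absolute difference stays at 0.6 − 0.15 = 0.45 mg/kg throughout. Only the relative contrast shrinks, and it matters only so far as the response depends on it.

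**Effect on a noninferiority claim.** The documents give no control rate, margin, alpha or share of children pre-treated, so all of these are assumed. Take a control rate p = 10%, margin M = 5 points, one-sided alpha 0.025 and 80% power with equal true rates:

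n per arm = (1.960 + 0.842)² × 2 × 0.10 × 0.90 / 0.05² = 7.85 × 0.18 / 0.0025, which is about 565.1 before rounding up, so 566.

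Suppose a fraction f of both arms is pre-treated and shows no arm difference at all, the most that prior steroid could do by dilution. A true excess equal to M then appears as (1 − f)M. The chance of falsely declaring noninferiority is Φ(fM/SE − 1.96), with SE² = [p(1 − p) + q(1 − q)]/n and q = p + (1 − f)M.

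At f = 5%: q = 0.1475, SE = √[(0.0900 + 0.1257)/566] = 0.0195, and Φ(0.0025/0.0195 − 1.96) = Φ(−1.83) = 0.034.

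| f (assumed) | False-noninferiority rate |
|---|---|
| 0 | 0.025 |
| 2% | 0.028 |
| 5% | 0.034 |
| 10% | 0.044 |
| 20% | 0.075 |

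With control rates from 5% to 15% and margins of 5 or 10 points, each with its own n, the rate is 0.032–0.034 at f = 5%, 0.040–0.045 at 10% and 0.063–0.077 at 20%.

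**In the vanguard.** If f is 2–10%, then 50 × 0.02 = 1 to 50 × 0.10 = 5 children are affected. At a 10% event rate, the 95% half-width for the difference is 1.96 × √(2 × 0.10 × 0.90/25) = 0.166, about 17 points. Diluting a 5-point difference by 10% moves it by 0.5 points, which could not be seen.

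**The case against.** The strongest reply is that the harm does not arise in this trial. The vanguard has no set margin, no alpha and no noninferiority test. The margin is still to come from physician surveys ("The noninferiority margin is the number of revisits/readmission for croup that clinicians can tolerate"), and the statistical section plans none. That stands: a reader might infer that the vanguard's own result would be biased toward noninferiority, and the documents give it no such result. Nor is carry-over into the definitive trial certain, since assessing eligibility criteria is one of the vanguard's aims. But the protocol does expect the same PICO, so the wording will pass on unless someone changes it.

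Four further inferences are tempting and not supported.

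- The Chart Review item "any corticosteroid treatment in hospital" might be read as a broader steroid rule that conflicts with the exclusion. It is a data item examined after day 30, not an eligibility criterion, so there is no contradiction.
- One might say that adverse events would all be put down to the study dose. The section on relationship to study intervention has the investigator weigh other drugs and concomitant treatments.
- One might say that pre-treated children could never be identified. Medical history is scheduled on Day 0, the list of other medications is open-ended, and concomitant medications are entered in REDCap. The full CRF and operations manual are not in the text reviewed, so a route item may already exist.
- The Rationale calls dexamethasone a long-acting systemic corticosteroid. That may support concern about an intramuscular dose. It does not show carry-over from a nebulised one.

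Finally, if the two doses truly do not differ, there is nothing to dilute.

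**Conclusion.** The gap is real: it appears in both statements of the exclusion, and no other criterion closes it. The direction is also right, because prior steroid in both arms favours a noninferiority conclusion. The size is unknown, as the documents do not say how many children arrive treated by an unlisted route. If that is 2–10% (an assumption), even a model that removes all arm difference in those children lifts the false-noninferiority rate only from 0.025 to about 0.028–0.044. The result also rests on the assumed control rate, margin and alpha.

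This is therefore a small improvement worth making because it is nearly free. It is aimed at the definitive trial and at any vanguard data pooled into it. The word internal in the design description may imply such pooling, but the text does not say so. It is not a flaw in a test within the 50-child vanguard.

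**What to change.** In the Exclusion criteria and in the Study Population row of the Protocol Summary, reword the item to cover corticosteroids by any systemic route, including intramuscular, within the same 72 hours. The sponsor should state whether nebulised corticosteroid is covered too.

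On the Baseline CRF, record the route and time of any corticosteroid given in that 72-hour window, if the form does not already ask. Any remaining exposure can then be described by arm.

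The cost is a few words in two places, at most one CRF item, and a few children lost to enrolment. The site counted 710 croup presentations between January 2021 and January 2022 against a target of 50, so the loss should be tolerable, although the protocol does name recruitment as a possible challenge.
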